#### **4.4.3 Prohibited Food**

- Consumption of methylxanthine-containing products (e.g., coffee, tea, cola, chocolate) will be forbidden from 48 hours prior to day of check-in to the CRU and during the stay.
- Alcohol consumption will not be permitted 96 hours prior to admission in the clinical unit and until discharge from the CRU.
- It is not permitted to take any nutrients known to modulate cytochrome CYP3A activity (e.g., grapefruit juice; Seville orange) within 2 weeks prior to first dosing until discharge from the CRU at the end of the study.

- To avoid false positive drug screen results, participants should refrain from consuming any foods containing poppy seeds within 48 hours (2 days) prior to screening and day of check-in for each treatment period.

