### **1.2.1.1 Clinical Pharmacology**

Exposure of balovaptan increased in a greater than dose-proportional manner following single doses of 0.5 to 76 mg, whereas an approximately linear increase in exposure was observed after repeated dosing with 12 to 52 mg once daily (qd) for 14 days. Balovaptan was rapidly absorbed with a median time to maximum observed plasma concentration (Tmax) between 1 and 4.5 hours after administration of single doses in fasted state and between 3 and 4 hours in the fed state following multiple dosing. Steady state was achieved after approximately 7 days; the mean apparent elimination half-life after the last dose (Day 14) was approximately 46 hours. Food had no relevant effect on the overall exposure of balovaptan. The terminal half-lives after 14 once daily dosing of balovaptan 10 mg for balovaptan, [REDACTED], respectively

In the human mass balance study (Study BP29279), an almost complete absorption of the study drug was observed within the first 72 hours following administration.

[REDACTED]

Mean cerebral spinal fluid (CSF)-to-plasma concentration ratios of balovaptan [REDACTED] following 7 days of dosing of 10 and 52 mg qd balovaptan were independent of dose.

[REDACTED]

Hepatic metabolism was found to be the major pathway of elimination [REDACTED]

[REDACTED] The majority of excretion occurred within the first 7 days.

There was no clinically/statistically relevant PK interaction with the P-glycoprotein substrate risperidone, one of only 2 approved medications for ASD symptoms in the US, and fluoxetine, a weak CYP3A4 inhibitor often used to treat associated symptoms of ASD. The presence of itraconazole led to a 5.6-fold increase in balovaptan exposure ( $AUC_{tau}$ ) and a 4.5-fold increase in  $C_{max}$  following multiple doses of 5 mg of balovaptan.

[REDACTED] The presence of rifampicin led to a 15-fold decrease in balovaptan exposure ( $AUC_{tau}$ ) and a 7.3-fold decrease in  $C_{max}$  following multiple doses of 10 mg of balovaptan. [REDACTED]

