### 3. STUDY DESIGN

#### 3.1 DESCRIPTION OF THE STUDY

This will be a single-center, part-randomized, open-label, single-dose, 3-period crossover study to investigate the effect of food and of esomeprazole on the PK of balovaptan in healthy volunteers.

Screening will be conducted between Day -28 and Day -2.

In Period 1, eligible subjects will be admitted to the clinical research unit (CRU) on Day -1 (the day prior to balovaptan dosing on Day 1) and will remain confined in the CRU until discharge on the morning of Day 5.

In Period 2, subjects will be re-admitted to the CRU on Day -1 (the day prior to balovaptan dosing on Day 1) and will remain confined in the CRU until discharge on the morning of Day 5.

In Period 3, subjects will return to the CRU for re-admission 5 days prior to administration of balovaptan (Day 9 of Period 2) to begin esomeprazole dosing. Esomeprazole will be dosed for 6 days: for 4 days prior to co-administration with balovaptan on Day 1 of Period 3, plus an additional dose on Day 2. Subjects will be discharged on Day 5.

In each period, following discharge from the CRU on Day 5, subjects will return to the CRU on Day 7 and Day 9 for further PK sampling.

There will be a washout of at least 12 days and up to 21 days between administrations of balovaptan. Thus, re-admission for Period 2 may be between 3 to 12 days after Day 9 of Period 1, and re-admission for Period 3 will be on Day 9 of Period 2.

Subjects will be randomized to 1 of 2 treatment sequences (ABC or BAC) on Day 1 of Period 1, with the treatments being as follows:

[figure not shown]
- Treatment A: 20 mg balovaptan administered as a single oral dose following consumption of high-fat, high-calorie meal
- Treatment B: 20 mg balovaptan administered as a single oral dose following a  $\geq 10$ -hour fast
- Treatment C: 40 mg esomeprazole administered once daily for 6 days and with a single oral dose of balovaptan 20 mg in the fasted state 1 hour after the fifth esomeprazole dose

During treatment periods 1 and 2, subjects will receive each of Treatment A or B, according to the randomization schedule. All subjects will receive Treatment C in Treatment Period 3.

Subjects will return for a follow-up visit on Day 16  $\pm$  2 of Period 3. Assessments during the study will be conducted according to the schedule of assessments ([Appendix 1](#)).

[Figure 1](#) presents an overview of the study design.

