#### **4.4.2 Prohibited Therapy**

Participation in an investigational drug study within 4 weeks or 5 times the elimination half-life, whichever is longer, prior to first dosing, or within 5 months prior to first dosing in case of a study with a biologic, as calculated from the day of follow-up from the previous study. Participation in an investigational device study within 4 weeks prior to first dosing is prohibited.

Any prescribed systemic or topical medication is prohibited within 4 weeks (or within 5 times the elimination half-life of the medication, whichever is longer) of the first dose administration, unless in the opinion of the Investigator the medication will not interfere with the study procedures or compromise safety, and slow release medicinal formulations considered to still be active within 4 weeks (or within 5 times the elimination half-life of the medication, whichever is longer) of the first dose administration are also prohibited unless in the opinion of the Investigator the medication will not interfere with the study procedures or compromise safety.

The following concomitant medications in particular are prohibited, unless an exception has been agreed as mentioned above.

- P-gp substrates
- Any inhibitor of CYP3A or CYP2C19 taken within 4 weeks (i.e. more than 5 half-lives) prior to study drug administration, including but not limited to the following drugs: ketoconazole, miconazole, itraconazole, erythromycin, clarithromycin, ranitidine, cimetidine, fluoxetine, fluconazole, fluvoxamine, until follow-up.

Any inducer of CYP3A or CYP2C19 taken within 4 weeks prior to study drug administration, including but not limited to the following drugs: rifampicin, rifabutin, glucocorticoids, carbamazepine, phenytoin, phenobarbital, and St. John's wort, until follow-up. Use of any nonprescribed systemic or topical medication or herbal remedies within 7 days before the first study drug administration through follow-up is prohibited, unless in the opinion of the Investigator the medication will not interfere with the study procedures or compromise safety.

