## Appendix 1: Schedule of Activities

	Scr	Period 1								Period 2								Period 3								F/U
	D -28 to -2	D -1	D 1	D 2	D 3 & 4	D 5	D 7	D 9	w/o	D -1	D1	D 2	D 3 & 4	D 5	D 7	D 9	D10 to D12	D 13 a	D -1 a	D 1	D 2	D 3 & 4	D 5	D 7	D 9	D16 ±2 or ET
Biochemistry	X	X				X				X				X		X			X				X			X
Urinalysis	X	X																								X
Coagulation	X	X																								X
Urine drug and alcohol screen l	X	X								X					X											
Serology	X																									
Pregnancy test m	X	X								X					X											X
FSH n	X																									
Genotyping sample		X																								
Adverse event monitoring	X	X	X	X	X	X	X	X		X	X	X	X	X	X	X	X	X	X	X	X	X	X	X	X	X

ET=early termination; F/U= follow-up; FSH=follicle-stimulating hormone; w/o=washout

- Day 13 of Period 2 is Day -1 of Period 3.
- Balovaptan will be administered following a high-fat, high-calorie meal (Treatment A) or after a ≥ 10 h fast (Treatments B and C). Subjects should fast for 4 hours after balovaptan administration and refrain from drinking for 1 hour prior to and 1 hour post dose.
- Esomeprazole will be administered 1 hour prior to balovaptan.
- Standardized meals will be provided at approximately 4 and 8 hours post-balovaptan dosing in each treatment period
- Samples at predose, and at 0.25, 0.5, 1, 1.5, 2, 2.5, 3, 3.5, 4, 5, 6, 8, 12, 16, 24, 36, 48, 72, 96, 144, and 192 hours post dose
- Samples at predose, 0.25, 0.5, 1, 1.5, 2, 3, 4, 6, 8 hours post dose of esomeprazole
- Height, weight, and BMI calculation at screening; only weight at all follow-up.
- Safety ECG will be performed in triplicate at Screening and on Day -1 of each period; at all other time points single ECGs will be performed.
- Body temperature and respiratory rate will be measured at Screening and Day -1 of each period only.
- Orthostatic challenge testing will be performed at screening.
- On Day 1, vital signs measurements will be performed at 1 hour post dose.
- Drugs of abuse (amphetamines [including ecstasy], barbiturates, benzodiazepines, cannabinoids, cocaine, cotinine, opiates, methamphetamines, and methadone).
- Serum pregnancy test performed on all female subjects at Screening and Day -1 of each treatment period (Day 13 of Period 2 is Day -1 of Period 3) and at follow-up.
- In postmenopausal women to confirm menopause

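### Section 4.4.3 most naturally ends the ban on CYP3A-modulating foods before the last two balovaptan samples of Treatment C, but not before those of Treatments A and B

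*Combined protocol and SAP*

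**What the plan says.** Section 4.4.3 (Prohibited Food) sets one continuous ban on nutrients that modulate CYP3A, with grapefruit juice and Seville orange as examples. It runs "within 2 weeks prior to first dosing until discharge from the CRU at the end of the study".

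Section 3.1 describes Period 3 with esomeprazole dosing before and with balovaptan, "plus an additional dose on Day 2. Subjects will be discharged on Day 5". For every period it then says that, "following discharge from the CRU on Day 5, subjects will return to the CRU on Day 7 and Day 9 for further PK sampling". Appendix 1 agrees: it has a Discharge row at Day 5, and Days 7 and 9 of Period 3 are ambulatory visits. Its sampling footnote ends with "24, 36, 48, 72, 96, 144, and 192 hours post dose".

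Treatment C is not randomised to a period: "All subjects will receive Treatment C in Treatment Period 3".

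The drug restrictions end later. In Section 4.4.2 the list of CYP3A and CYP2C19 inhibitors closes with "fluoxetine, fluconazole, fluvoxamine, until follow-up", and the inducers carry the same end point.

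**The concern.** If discharge at the end of the study means the Day 5 discharge of Period 3, the food rule differs between the two arms of a primary comparison. Days 5 to 9 of Periods 1 and 2, where A and B are given, lie inside the ban. Days 5 to 9 of Period 3, where every subject has had C, lie outside it. The 144 h and 192 h samples of the test arm would be unprotected and those of the reference arm protected.

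The pathway matters for this drug. Section 1.2.1.1 names hepatic metabolism as the major route of elimination and reports strong sensitivity to CYP3A modulation: "The presence of itraconazole led to a 5.6-fold increase in balovaptan exposure" (AUCtau), and rifampicin lowered it 15-fold.

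A change in elimination after Day 5 would enter AUC0-inf, AUClast, half-life and CL/F for C only. Of these, AUC0-inf is one of the two parameters in the formal C versus B analysis. The model for that contrast in Section 6.6 has no period term, and adding one would not help, because C occurs only in Period 3. Appendix 1 lists no diet record from which exposed subjects could be identified later.

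**Working it through.** **Inputs from the protocol**
- Half-life about 46 h, measured after 14 days of dosing (Section 1.2.1.1). No single-dose value is visible in the public text.
- Last discharge on Day 5, that is 96 h after dosing; later samples at 144 h and 192 h (Section 3.1, Appendix 1).
- Residual CV 14%, 12 subjects, 90% CI, stated factor 1.11 (Section 6.1).

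**Assumptions, not in the protocol**
- The effect of diet on balovaptan clearance, and the share of subjects who would eat such foods between Days 5 and 9.
- The range of half-lives tried.

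**1. The plan's own figure.** s = sqrt(ln(1 + 0.14²)) = 0.139. The factor is exp(t × s × sqrt(2/12)). With 10 degrees of freedom it is 1.109, and with 11 it is 1.108. Both round to the stated 1.11, so the figure reproduces.

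**2. Share of AUC0-inf after the Day 5 discharge.** For a single exponential the share is exp(−ln2 × 96 / t½).
- t½ = 46 h: 0.235, of which 0.180 falls between 96 and 192 h and 0.055 is extrapolated.
- t½ = 30 h: 0.109. t½ = 60 h: 0.330.
- Over a wider assumed range of 24 to 72 h: 0.06 to 0.40.

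**3. Effect in one exposed subject.** If clearance falls by a fraction x from 96 h on, AUC0-inf is multiplied by 1 + 0.235 × (1/(1 − x) − 1).
- x = 0.1: 1.026. x = 0.2: 1.059. x = 0.3: 1.101.

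A noncompartmental calculation on the protocol's sampling times gives nearly the same: 1.027, 1.060 and 1.102. It assumes a one-compartment oral profile with absorption rate 1/h and takes the terminal slope from the last three points. For AUClast the multipliers are 1.011, 1.023 and 1.037, so much of the effect comes through the extrapolated tail. A clearance rise of 25% gives 0.952 for AUC0-inf, so the direction is not fixed.

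**4. Effect on the C/B geometric mean ratio.** If a share p of subjects is exposed, the ratio is multiplied by (individual multiplier)^p. With t½ = 46 h:

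| Assumed clearance fall | All exposed | 50% exposed | 25% exposed |
|---|---|---|---|
| 10% | 1.027 | 1.013 | 1.007 |
| 20% | 1.060 | 1.029 | 1.015 |
| 30% | 1.102 | 1.050 | 1.025 |
| 50% | 1.239 | 1.113 | 1.055 |

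With 25% exposed and falls of 10% to 30%, the mean shift is 0.2% to 0.7% at a 24 h half-life and 1.1% to 4.0% at 72 h.

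**5. Comparison with planned precision.** The group-level figures in step 4, not the individual ones in step 3, are what should be set against 1.11. The shift gets near 1.11 only if essentially all subjects have a clearance fall of about 30%, or half of them a fall of about 50%.

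**The case against.** **The wording may not mean Day 5.** Where the protocol means an ordinary discharge it says so more simply: the alcohol bullet in Section 4.4.3 stops at CRU discharge, and the exercise bullet in Section 4.4.4 stops at discharge in each period. The food bullet adds a reference to the end of the study. Section 3.2 ties that to last observation or safety follow-up, and Section 4.6.2 has subjects come back to the CRU for follow-up. Exclusion criterion 28 in Section 4.1.2 asks subjects to agree to avoid prohibited food during the study. Release at the follow-up visit is therefore a possible reading, and under it there is no asymmetry.

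This stands in part. A reader might infer that the plan certainly leaves the Treatment C tail unprotected; the documents do not go that far. Day 5 remains the more natural reading. The Discharge row stops there, Section 4.4.2 names follow-up when that is what it means, and criterion 28 refers to prohibited food without giving an end date of its own.

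**No document supports a size.** The protocol gives neither a dietary effect on clearance nor an intake rate. The itraconazole result concerns a drug inhibitor with repeated balovaptan doses; it shows sensitivity to CYP3A but does not measure what food begun 96 h after one dose would do. Absorption is almost complete by 72 h (Section 1.2.1.1), so only systemic elimination could still change. This stands in full.

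**An esomeprazole effect would still show.** A reader might infer that the gap could hide the reduction in exposure that Section 3.3.1.1 considers possible. The documents do not support that. The mechanism of concern is pH-dependent absorption, Cmax is analysed alongside AUC0-inf, and AUC0-24h and Tmax are also estimated. Food eaten after 96 h can affect none of these three. The tail could also move either way.

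**Conclusion.** The concern holds as a point of unclear wording that, on its most natural reading, treats the last two samples of Treatment C differently from those of A and B. At a 46 h half-life about 23.5% of AUC0-inf lies after the ban would end. The C/B results for AUC0-inf, AUClast, half-life and CL/F could be shifted up or down, and no model term can remove the shift.

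The expected size is probably small, about 0.7% to 2.5% in the mean if a quarter of subjects had a clearance fall of 10% to 30%. That is well inside the planned factor of 1.11. It rests on the 46 h multiple-dose half-life, single-exponential decline, and assumed dietary effects and intake. Cmax, AUC0-24h and the food contrast A versus B are unaffected. This is a cheap improvement, not a flaw that threatens the trial's conclusions.

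**What to change.** Reconcile the food bullet in Section 4.4.3 with the discharge and sampling days in Section 3.1 and Appendix 1 and with the end point used for drugs in Section 4.4.2. State explicitly either that the restriction on CYP3A-modulating foods covers the last PK sample of Period 3 (Day 9), or that it runs until follow-up as for CYP3A drugs.

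The cost is one sentence of protocol text and the matching subject instruction. Compared with release on Day 5, subjects keep the restriction for four more days (Day 5 to Day 9), or for 9 to 13 more days if it runs to follow-up (Day 16 ± 2, so Day 14 to Day 18). Sample size, sampling times and the analysis model do not change. With all three treatments covered alike, this source of bias is removed.

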#### 4.4.4 Additional Restrictions/Considerations

- For Treatment A, high-fat, high-calorie breakfast with calculated calorific content will be provided. An example of a high-fat, high-calorie meal is provided in [Table 2](#); components of the high-fat breakfast may be substituted as long as the total calorie content from fat, carbohydrates, and protein is approximately the same as listed. The high-fat, high-calorie meal should be consumed within 30 minutes.
- On Day 1 of each study period, meals standardized with regard to timing and content will be provided at approximately 4 and 8 hours post-balovaptan dosing.
- On all other days during confinement, there are no specific meal requirements; meals and snacks will be provided according to PRA SOPs.
- Subjects should refrain from strenuous exercise at least 72 hours prior to dosing until discharge from the unit in each period.
- While in the CRU, subjects will be allowed to consume water ad libitum, except for 1 hour before and 1 hour after oral dosing with balovaptan. Subjects will be provided guidance at CRU admission, for each treatment period, that they should avoid excessive fluid intake during the study. Excessive fluid intake for this study is defined as 3 L (100 fl oz) per day. Clinic staff will provide guidance as to approximate number of drinks in 3 liters as part of the subject orientation process at admission. However, the clinical site will not be required to measure, or record fluid intake.
- Alcohol consumption will not be allowed 96 hours before the day of admission to the CRU and while staying in the CRU. Additional alcohol/drugs of abuse testing may be employed throughout the study to verify compliance. For other days during the study, alcohol must be restricted to no more than 2 drinks per day (one drink is equal to 12 ounces of beer, 5 ounces of wine, or 1.5 ounces of 80 proof spirits).

**Table 2 Example of a Standard High-Fat, High-Calorie Breakfast**

Food item	Calories	Fat (g)	Carbohydrates (g)	Protein (g)
2 large eggs fried in 14 g (1 Tbsp) of butter	219	19	0	12
4 strips bacon	140	12	0	8
½ cup (115 g) fried hash brown potatoes	128	0	26	6
2 slices toasted wheat bread	129	1	22	8
4 packets of butter, 5 g each	144	16	0	0
8 oz whole milk	148	8	11	8
Totals	908	56	59	42

## 4.5 STUDY ASSESSMENTS

The schedule of activities to be performed during the study is provided in [Appendix 1](#). All activities must be performed and documented for each subject.

Subjects will be closely monitored for safety and tolerability throughout the study.

#### **4.5.1 Informed Consent Forms and Screening Log**

Written informed consent for participation in the study must be obtained before performing any study-related procedures (including screening evaluations). Informed Consent Forms for enrolled subjects and for subjects who are not subsequently enrolled will be maintained at the study site.

All screening evaluations must be completed and reviewed to confirm that subjects meet all eligibility criteria before enrollment. The Investigator or designee will maintain a screening log to record details of all subjects screened and to confirm eligibility or record reasons for screening failure, as applicable.

#### **4.5.2 Medical History, Baseline Conditions, Concomitant Medication, and Demographic Data**

Medical history, including clinically significant diseases, surgeries, cancer history (including prior cancer therapies and procedures), reproductive status, smoking history, and use of alcohol and drugs of abuse, will be recorded at baseline. In addition, all medications (e.g., prescription drugs, over-the-counter drugs, vaccines, herbal or homeopathic remedies, nutritional supplements) used by the subject within 4 weeks prior to initiation of study treatment will be recorded.

Demographic data will include age, sex, and self-reported race/ethnicity.

#### **4.5.3 Physical Examinations**

A complete physical examination will be performed at screening and at the follow-up visit ([Appendix 1](#)). The examination should include an evaluation of the head, eyes, ears, nose, and throat; and the cardiovascular, dermatologic, musculoskeletal, respiratory, gastrointestinal, and genitourinary (at the Investigator discretion) systems. Any clinically significant abnormality identified at baseline should be recorded on the General Medical History and Baseline Conditions eCRF. Changes from baseline abnormalities should be recorded in subject notes. New or worsened clinically significant abnormalities should be recorded as adverse events on the Adverse Event eCRF and source form.

#### **4.5.4 Vital Signs**

Oral body temperature, pulse rate, blood pressure, and respiratory rate will be measured at the time points described in [Appendix 1](#). Blood pressure and pulse rate measurements will be performed after the subject has rested in a supine position for at least 5 minutes.

##### **4.5.4.1 Orthostatic Challenge Testing**

Orthostatic challenge testing will be performed at Screening.

During a 15-minute period during which subjects will remain in a supine position, blood pressure according to the Riva-Rocci method and pulse rate will be measured after 10 and 15 minutes. If the second blood pressure measurement deviates from the previous measurement by more than 5 mmHg, another 5-minute extension period will be added, and blood pressure and pulse rate will be obtained after 20 minutes in the supine position.

The subject will then be asked to erect rapidly into a standing position, and blood pressure and pulse rate will be assessed again after 3 minutes of standing.

Standing blood pressure and pulse rates will be compared against the latest blood pressure and pulse rate values obtained in the supine position. Orthostatic hypotension is defined as a decrease in systolic blood pressure by at least 20 mmHg and/or a decrease in diastolic blood pressure by at least 10 mmHg.

Such changes used to define orthostatic hypotension or pre-syncopal/syncopal events during standing will result in exclusion.

